Title: *Morning bright light to improve sleep quality in Veterans*

Publications:

Data collection ongoing.

Relevance:

This protocol has recruited 91 participants over 18 months, 60 of which underwent MBLT for 4 weeks. The primary purpose of this protocol was to assess feasibility outcomes, including recruitment rate, retention rate, and adherence to the light therapy. Of the participants with TBI, 88% of subjects remained adherent to light therapy for the full 4 weeks. Overall, 91% of subjects said they liked using the lightbox. We additionally found that MBLT improves self-reported sleep, mood, and quality of life in our pilot cohort, however, this study lacks a placebo device for comparison.

Research Design and Methods:

Veterans within the VA Portland Healthcare System (VAPORHCS) and non-Veterans will be recruited for participation in this study. This study will consist of at least 4 visits over the span of ~5-6 mo.

Study Overview and Timeline.

	Visit 1	Visit 2	At Home	Visit 3	Visit 4 Follow up
Time point:	Day 0	Week 2	Week 2-6	Week 6	Week 10
Informed consent	X				
Subject given actiwatch		X		X	
Conduct pain assessment		X		X	X
Subject given lightbox or sham		X			
Questionnaires		X		X	X
Daily use of intervention for 1 hour			X		
Total time	~120 min	~120 min	28 hours	~120 min	~120 min

- *Informed consent and HIPAA authorization.* Written and verbal informed consent will be obtained before all other Visit 1 activities and may take place on an earlier date if DocuSign is able to be used to facilitate the consent conversation.
 - In cases where DocuSign is not feasible, consent conversations will take place in office space available at the VAPORHCS Sleep Disorders Clinic (building 100-6C), in related outpatient clinical space, or in Research Service space approved for human subjects use

(building 101, rooms 432A, 430, 404), or in subjects' homes. Alternatively, consent may take place remotely via phone or video conferencing via mailed documents.

- Where DocuSign is feasible, study staff will initiate email of a DocuSign envelope providing subjects access to the consent and authorization forms ahead of the consent discussion. Subjects will then be guided through downloading the fully executed consent form.

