Video Conferencing. If the subject is comfortable and equipped, we may conduct visits using video conferencing, such as VA Video Connect or other VA approved methods (skype, facetime, google hangouts, etc.). A link to the video chat will be emailed participants via Azure RMS encrypted email. For VA Video Connect (VVC), this email is entered into the VCC platform and an email is automatically generated.

At home visits. In special circumstances study personnel may travel to the subject's homes in order to conduct the visit more comfortably. Equipment, data, and specimens will travel in between the home and the VA only.

Phone calls. In between visits subjects will be contacted up to 2 times per week as needed. They will be assessed for understanding and compliance and given the opportunity to asked questions. Questions will be asked about their sleep, pain, and quality of life metrics.

Emails. Communication via RMS Azure encrypted email may be established between the subject and study coordinator in order to allow subjects to freely ask any questions they may have.

Study Population:

Number of subjects. The target population will consist of n=100 subjects. In order to meet this enrollment target we anticipate that up to 400 individuals may need to be recruited (consented) and screened.

Eligibility Criteria. Only Veterans and non-Veterans who are physically and mentally able to provide written and verbal informed consent and have a medical record-confirmed or physician confirmed diagnosis of TBI, will be included in this study. Additional criteria are as follows:

- 1) Current self-reported sleep-wake disturbances (defined by clinically abnormal Insomnia Severity Index and/or Functional Outcomes of Sleep scores)
- 2) Moderate to severe pain (defined as a score of ≥ 4 on an 11-point scale⁹⁰) persisting for longer than 6 months
- 3) Do not have a diagnosis for dementia
- 4) Are not currently using a lightbox or negative ion generator
- 5) Are not night-shift workers
- 6) Are English speaking with phone access
- 7) Are 18 years of age or older
- 8) Do not have macular degeneration or bipolar disorder (both are relative contraindications to regular bright light exposure)
- 9) No suicidal ideation
- 10) No cancer diagnosis in the past 6 months
- 11) At least 6-12 months of being surgery free
- 12) No evidence of drug and alcohol dependency (defined by the substance abuse and dependency scale).
- 13) Are currently living within the United States.

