Our inclusion/exclusion criteria will not exclude any specific class of persons who might benefit from the proposed research. Every effort will be made to include women and minority groups in this study. All Volunteers meeting inclusion/exclusion criteria will be invited to participate in the study, regardless of gender or racial/ethnicity status. Women comprise 8.5% of the Veterans included in the established VAPORHCS Sleep Disorders Data Repository (MIRB #3636) and minorities 8.3%. The same inclusion/exclusion criteria are applied for all participants which ensures that there is no recruitment bias to confound the results.

Every effort will be made to recruit Veterans for the completion of this project. However, we will plan to recruit non-Veterans as necessary to ensure sufficient data to answer study questions. The Veteran population is disproportionately male and often burdened with significant health issues. Thus, the inclusion of non-Veteran recruitment will help ensure greater recruitment eligibility and enrich for the inclusion of more women and underrepresented minorities. While we will not specifically target active military personnel for recruitment, we will also include them when they reach out to project staff about participating.

Power analysis. From pilot data collected via MIRB #4085, as well as from literature regarding MBLT interventions, a power analysis was conducted in order to estimate the sample size needed to detect a statistically robust difference in the described primary outcome variables at an acceptable level of significance and power with a clinically meaningful level effect size. In order to account for the inclusion of the sham control, a placebo effect size was postulated at 50% of the observed MBLT effect with the same variance in outcomes as observed in the pilot cohort. This led to a postulated collection of effect sizes necessary to observe differences in the various outcomes between the MBLT and a sham control. Most fell between 0.5

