and 1.0, after including a sham control group with postulated, one-treatment per arm sample sizes of 20-70, with a mean sample size of 47 and median of 50 post drop-out. This is consistent with prior studies that examined efficacy of MBLT therapy within comparable populations (e.g., circadian rhythm sleep disorders, insomnia, depression, or dementia), showing Hedges' g effect sizes ranging from 0.20 to 0.95 in sample sizes ranging between $n = 26$ to 42.³¹ Therefore, we intend to recruit 50 subjects per group. This sample size should be sufficient to detect clinically meaningful shifts in our outcome variables at levels that are robust enough to be accurately modeled and statistically evaluated.

Subject Identification/Recruitment

Research subjects will be recruited through word of mouth and several other methods:

1. **Repositories:** Participants may be recruited from an existing data repository at VAPORHCS (VA MIRB #3636, PI: [name], n=670 participants or VA MIRB #4086, PI: [name], n=200), approximately 30% of whom report TBI. These individuals have all provided informed consent for their data to be kept in the data repository and have given their permission to be re-contacted for future research studies.
2. **Sleep Clinic:** Veterans may be recruited from the VAPORHCS Sleep Disorders Clinic, or other outpatient clinics at VAPORHCS that have referred participants to us. Veterans will be approached in person or called on the phone, evaluated for eligibility in this study, and if interested, invited to undergo verbal and written informed consent.
3. **Flyers:** Volunteers may be recruited by fliers posted within the VAPORHCS, OHSU, and in the community. In the Portland VA, these flyers will be posted in the building 104 elevator, in handout stands in various clinics, and other VA bulletin boards with approved space for research flyers. They will also be given to clinicians at outpatient clinics to give to interested subjects. Interested subjects who contact us will then be screened over the phone with our phone script. If the participant is eligible and interested after the phone screen, we will plan to meet in person at VAPORHCS to get written and verbal informed consent.

Informed Consent & HIPAA Authorization:

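### The power analysis gives a median of 50 per arm after drop-out and recruits the same 50 per group, without stating a drop-out rate or the number expected in the analysis

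*Protocol*

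**What the plan says.** All the sample-size statements are in the protocol's Study Population section.

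- **Number of subjects** sets the total: "The target population will consist of n=100 subjects". It adds: "In order to meet this enrollment target we anticipate that up to 400 individuals may need to be recruited (consented) and screened".
- **Power analysis** says the calculation was made "at an acceptable level of significance and power with a clinically meaningful level effect size". No numeric alpha, sidedness or power is given.
- On effect sizes it reports a range of 0.5 to 1.0 for most outcomes. The corresponding per-arm numbers run from 20 to 70 and are summarised in these words: "with a mean sample size of 47 and median of 50 post drop-out".
- The same paragraph concludes: "Therefore, we intend to recruit 50 subjects per group".

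The Preliminary Studies section describes a feasibility pilot whose aims included retention and adherence as separate outcomes. The one relevant pilot figure for TBI is on adherence: "Of the participants with TBI, 88% of subjects remained adherent to light therapy for the full 4 weeks". No retention figure is reported. The protocol contains no drop-out rate, no inflation step and no rule for replacing participants who leave after enrolment.

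**The concern.** In ordinary usage, a size after drop-out is what remains and a number recruited is what enters. The paragraph gives the same value, 50 per arm, to both, and nothing stands between them. Some loss is foreseeable: the device is used at home for an hour each morning over four weeks, outcomes are taken at Visit 3 and again about four weeks later at Visit 4, and participants may withdraw at any time.

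At stake is what the stated size supports. The paragraph ends by calling 50 per group sufficient for clinically meaningful shifts in the outcomes. A reader cannot tell whether that refers to 50 people analysed or to some smaller unstated number. The difference matters most for outcomes near the lower end of the protocol's effect range, where the margin is thinnest.

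**Working it through.** **Inputs from the protocol.** Sizes of 20 to 70 per arm across outcomes, mean 47, median 50 (Power analysis); 50 per group to recruit (Power analysis); 100 in total (Number of subjects); standardised effects mostly 0.5 to 1.0 (Power analysis).

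**Inputs assumed here, because the protocol gives none.** Two-sample t-test with equal arms, two-sided 5%, 80% power, loss between 5% and 20%.

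**Step 1: the plan's own figures.** The total reproduces: 2 × 50 = 100. The median of 50 cannot be reproduced, because alpha, power, drop-out and the effect for each outcome are not given. The range 20 to 70 is of the right order: under the assumed settings an effect of 0.5 needs 64 per arm and an effect of 1.0 needs 17.

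**Step 2: number left.** Analysed per arm = 50 × (1 − loss), rounded down.

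**Step 3: detectable effect and power.** The approximate detectable effect at n per arm is (1.960 + 0.842) × √(2/n). At n = 50 this is 2.802 × 0.200 = 0.560. The exact t-test calculation, with 2n − 2 degrees of freedom and noncentrality d × √(n/2), gives 0.566. The table uses the exact version.

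| Assumed loss | Analysed per arm | Detectable effect, 80% power (SD) | Power at 0.5 SD |
|---|---|---|---|
| 0% | 50 | 0.566 | 70% |
| 5% | 47 (47.5) | 0.584 | 67% |
| 10% | 45 | 0.597 | 65% |
| 15% | 42 (42.5) | 0.619 | 62% |
| 20% | 40 | 0.634 | 60% |

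**Step 4: recruitment needed to have 50 left.** 50 / (1 − loss): 50/0.95 = 52.6, so 53 per arm (106 in total) at 5%; 50/0.90 = 55.6, so 56 (112) at 10%; 50/0.80 = 62.5, so 63 (126) at 20%.

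**Step 5: does the other reading fit?** Suppose the stated sizes already include an allowance. Dividing the Step 1 sizes by 0.9 (10% loss) gives 64/0.9 = 71.1 and 17/0.9 = 18.9, close to the stated 20 to 70. The figures therefore do not exclude this reading. They do not establish it either, since the alpha, power and loss rate used are unknown.

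**The case against.** The strongest reply is that *post drop-out* was meant as *after adjusting for drop-out*. Step 5 shows that this is compatible with the protocol's range. On that reading 50 is the inflated number, the conclusion to recruit 50 follows, and there is no shortfall. This stands as a possibility. A reader might infer that the trial can reach its planned size only if nobody drops out; the documents do not support putting it so flatly. What remains on this reading is that the analysed number is below 50 and is not stated.

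Second, 50 is not one required size for a named outcome. It is a median over outcomes. Against the mean of 47, a loss of 3 in 50 (6%) is absorbed, and outcomes needing 40 or fewer are covered even at 20% loss. This also stands. Equally, a median of 50 means that about half the outcomes need 50 or more before any loss.

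Third, one might read the pilot's 88% as expected retention and compute 44 per arm. The documents do not support that: the figure is adherence to the light, and someone who stops using the device can still attend visits and be analysed. Nor does the protocol claim 80% power for any particular effect, so a statement that power falls from 80% to some lower figure would start from a claim that was never made.

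Finally, the 400 to be consented and screened might seem to supply the allowance. They are described as what is needed to reach the enrolment target, so they cover losses before enrolment. They do show that the protocol uses the word recruit for both 400 and 100, which adds to the need for labels.

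**Conclusion.** The point holds as a defect in how the sample size is stated. The paragraph gives 50 per arm both as a size after drop-out and as the number recruited, and states no drop-out rate, allowance or expected analysed number. On the plain reading any loss takes the trial below its stated median size. On the alternative reading the size is coherent, but the number it rests on is unreported. Neither reading lets the reader check the claim of sufficiency.

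The likely effect is modest. Under the assumed settings the detectable effect rises by at most about 0.07 SD (0.634 against 0.566), and power at an effect of 0.5 falls by about 3 to 10 percentage points from 70%. On the alternative reading these figures describe what 50 enrolled would deliver, not a shortfall against the plan. All of them depend on the assumed alpha, power and loss range and would change with the sponsor's own values. They do not show that the trial is inadequately sized for its outcomes as a whole.

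**What to change.** Keep 100 enrolled and revise the Power analysis paragraph to:

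1. label each of 20 to 70, 47 and 50 as a number enrolled or a number analysed;
2. state the assumed drop-out rate, taken from the pilot's retention data and not from its 88% adherence figure;
3. give the expected analysed number per arm, 50 × (1 − that rate);
4. restate the detectable effect at that number, with the alpha, sidedness and power used.

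The cost is one or two sentences and a slightly less favourable stated detectable effect. If the sponsor confirms that 50 must remain after losses and prefers to protect that number, the alternative is to enrol more: 106 to 126 in total for 5 to 20% loss. The wording problem does not by itself require this.

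### Required sizes run up to 70 per arm, yet 50 per group is called sufficient for the outcomes without exception; an outcome needing 70 has about 66% power at 50 (78% if 70 was set for 90%).

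*Protocol*

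**What the plan says.** Under Study Population, the protocol sets the overall size: "The target population will consist of n=100 subjects". The Power analysis paragraph says that the calculation drew on pilot data and published light-therapy studies. It was meant to find the size needed for the primary outcome variables (plural) "at an acceptable level of significance and power with a clinically meaningful level effect size". No number is given for alpha, sidedness, power or drop-out.

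The sham effect is taken as half the pilot effect with the same variance. This yields a set of "effect sizes necessary to observe differences in the various outcomes between the MBLT and a sham control". On their size the text says "Most fell between 0.5" and, continuing over the page, "and 1.0, after including a sham control group". The corresponding per-arm figures are "sample sizes of 20-70, with a mean sample size of 47 and median of 50 post drop-out". The choice follows: "Therefore, we intend to recruit 50 subjects per group". The paragraph closes with the claim at issue: "This sample size should be sufficient to detect clinically meaningful shifts in our outcome variables at levels that are robust enough" (the sentence goes on to say robust enough for modelling and testing). It does not say which outcomes need more than 50 per arm or what power they would have.

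**The concern.** The chosen size is the median of the sizes that the plan derived for its own outcomes. A median size covers the outcomes at or below it and leaves the rest short. The concluding sentence nevertheless speaks of the outcome variables in general.

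The three Specific Aims (sleep quality, pain, quality of life) each carry a hypothesis, and the power paragraph singles out no one outcome. A reader therefore cannot tell which hypotheses are tested at the intended power. If an outcome above the median gives a null result, the protocol's wording invites the reading that the trial was large enough to find a meaningful effect and found none. For that outcome the plan's own calculation says otherwise.

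**Working it through.** **Inputs from the protocol (Power analysis; Number of subjects).** Per-arm sizes 20 to 70, mean 47, median 50; most effect sizes 0.5 to 1.0; 50 per group, 100 in total.

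**Assumptions.** Alpha and power are not stated. I take a two-sample comparison of means with equal arms at two-sided 5%, and run targets of 80%, 85% and 90%. One-sided 5% is shown as a check.

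**Step 1: can the 20-70 range be reproduced?** Not strictly, because alpha, power and drop-out are missing. Normal-approximation sizes per arm for d = 1.0 and d = 0.5 come close under several settings:

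- 80%, two-sided: 16 and 63. Divided by 0.9 for an assumed 10% drop-out: 16/0.9 ≈ 18 and 63/0.9 = 70.
- 85%, two-sided: 18 and 72.
- 90%, one-sided: 18 and 69.

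So 20-70 is what one would expect if these are required sizes for effects of about 1.0 down to 0.5.

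**Step 2: how many outcomes exceed 50?** A maximum of 70 means at least one does. A median of 50 means at most half do. The exact count cannot be recovered, because neither the number of outcomes nor ties at 50 are given.

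**Step 3: power at 50 per arm for an outcome that needs 70.** The effect for which n per arm is just enough is d = (z for alpha + z for power) × √(2/n). Power at 50 per arm is Φ(d × √(50/2) − 1.960), and √(50/2) = 5.

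- Set for 80%: d = (1.960 + 0.842) × √(2/70) = 0.474; power = Φ(0.474 × 5 − 1.960) = Φ(0.41) ≈ 65.8%.
- Set for 90%: d = (1.960 + 1.282) × √(2/70) = 0.548; power = Φ(0.548 × 5 − 1.960) = Φ(0.78) ≈ 78.2%.

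The t-test (noncentral t) gives 65.6% and 78.0%, and 71.4% for an 85% target. One-sided 5% gives 67.4%, 73.1% and 79.5% for the three targets. Every value is below the target used to set 70.

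**Step 4: outcomes between 50 and 70 (t-test, two-sided 5%).**

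| Required per arm | d if set for 80% | Power at 50 | d if set for 90% | Power at 50 |
|---|---|---|---|---|
| 55 | 0.539 | 76% | 0.624 | 87% |
| 60 | 0.516 | 72% | 0.597 | 84% |
| 65 | 0.495 | 69% | 0.573 | 81% |
| 70 | 0.477 | 66% | 0.552 | 78% |

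The largest shortfall is 80 − 66 = 14 points, or 90 − 78 = 12 points.

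**Step 5: the same check from the effect sizes.** At d = 0.5, the lower end of the plan's main range, 50 per arm gives 69.7% power two-sided (79.9% one-sided). Two-sided, 63.8 per arm are needed for 80% and 85.0 for 90%. With 50 per arm analysed, the detectable d is 0.566 at 80% and 0.655 at 90%, both above 0.5.

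**Step 6: drop-out.** The label on the median can mean completers or an inflated number.

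- Both 70 and 50 are recruited numbers: a common drop-out rate cancels, and power stays at about 66% or 78%.
- 70 means completers and 50 means recruited: an illustrative 12% loss (borrowed from the 88% pilot adherence figure, which is not a drop-out rate) leaves 50 × 0.88 = 44 per arm, with power of about 60% or 73%.
- 70 is inflated for drop-out and 50 is the number analysed: an assumed 10-20% loss gives about 70-75% or 82-86%.

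No reading brings power up to its own target.

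**The case against.** The strongest counter-argument is about how to read the paragraph. The sample sizes are called postulated and the effect sizes are called necessary, so the sizes could be inputs and the effects what each size can detect. The numbers allow this: at two-sided 5% and 80% power, 20 and 70 per arm detect 0.91 and 0.48; at 90% they detect 1.05 and 0.55. No outcome would then need 70, and 50 per arm would detect about 0.57 to 0.65, inside the plan's range. This reading is hard to sustain. The stated purpose is to estimate the size needed for the outcomes. A mean of 47 and a median of 50 make sense as a summary of one size per outcome, not of a grid of trial sizes. The choice of 50 is drawn as a consequence of those figures.

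A second argument is that the claim is hedged, names no power level, and that taking a central size across several outcomes is a common compromise, visible two sentences earlier. Part of this stands: the range is disclosed, 50 may be a reasonable choice, and on a 90% target the worst case still has 78%. But the hedge softens certainty without narrowing scope, and the protocol does not present 50 as a compromise.

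Third, the exact figure depends on unstated inputs. That is correct. The milder drop-out reading, with 50 as the number analysed, fits poorly with a protocol that says 50 per group will be recruited and treats 100 as the enrolment target.

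Finally, alpha, power and power per outcome may be in an analysis plan that is not shown. Their absence is not the point here. The point is a claim the protocol makes that its own numbers do not support.

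**Conclusion.** The concern holds. Fifty per group is not sufficient, at the power the plan itself aimed for, for any outcome whose required size exceeds 50. That is at least one outcome and at most half. The direction needs no assumption about alpha or power, only that the 20-70 figures are required sizes per outcome, which is the natural reading.

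The size of the shortfall does need assumptions. At two-sided 5%, with 70 and 50 counted on the same basis, power for the worst outcome is about 66% against 80%, or 78% against 90%. It is 66-80% over targets of 80-90% and one- or two-sided tests. The drop-out readings widen this to about 60-86%. For outcomes just above 50 the loss is slight. This should be corrected, but it does not call the sample size itself into question.

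**What to change.** Keep 100 subjects and restrict the closing statement of the Power analysis paragraph. Suggested wording, with brackets filled from the calculation actually done:

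> With 50 subjects per group, [outcomes requiring 50 or fewer per arm] are covered at [planned power] with alpha [value, sidedness]. [Outcomes requiring more than 50, up to 70] have about [x]% power at 50 per group and are not regarded as adequately powered. With [N] per group expected to be analysed, the detectable standardised difference is [d].

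For illustration only: with 50 per group analysed at two-sided 5%, d is about 0.57 at 80% power and 0.65 at 90%. The same edit should say whether 50 is counted before or after drop-out, since the present wording can be read either way.

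The cost is protocol wording only: no added subjects, visits or procedures. The stated sensitivity becomes less favourable for the outcomes that need more than 50 per arm.
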